5.5.3.3. Electrocardiogram

Not applicable.

5.5.3.4. Other Safety Parameters

Not applicable.

5.6. Other Analyses

5.6.1. Pharmacokinetics

Not applicable.

5.6.2. Immunogenicity

Not applicable.

5.6.3. Pharmacodynamics

Not applicable.

5.6.4. Pharmacokinetic/Pharmacodynamic Relationships

Not applicable.

5.6.5. Biomarkers

Not applicable.

5.6.6. Health Economics

Not applicable.

5.6.7. Other Variables and/or Parameters

Not applicable.

5.6.8. Definition of Subgroups

The following subgroup will be used for some of the safety endpoints, i.e., TE-AE, TE-SAE, severe TE-AEs, related TE-AEs, TE-AESIs, Death and TE- marked laboratory abnormalities.

| Subgroup | Definition |
|---|--|
| *Concomitant PAH-specific medication (group 1), Section 6.5 | 
 • No PAH-specific medication (ERA or PDE5-I) • Endothelin receptor antagonist (ERA) alone • Phosphodiesterase 5 inhibitor (PDE5-I) alone • Combination of both ERA and PDE5-I |

*For both STS (A302+A303) and OLS, this variable should be re-baselined according to Sections 6.3 and 5.1.5

In addition to the subgroups defined above, the following “potential” subgroups defined by selected baseline characteristics will be set up in the ADaM dataset.

| (Potential) Subgroup | Definition |
|--|---|
| Gender | 
 • Male • Female |
| *Age Group at baseline (years) | 
 • [<18] • [18-64] • [65-74] • [75-84] • [\geq85] |
| *WHO Functional Class at baseline (group 1) | 
 • I/II • III/IV |
| *WHO Functional Class at baseline (group 2) | 
 • I • II • III • IV |
| *Concomitant PAH-specific medication (group 2) | 
 • No PAH-specific medication • 1 PAH-specific medication • \geq 2 PAH-specific medications 
The number of PAH specific medications (type) is based on following 4 types.
 
 - ERA - PDE5-I - sGC stimulator - Prostacyclin |
| Etiology | 
 • Idiopathic, heritable, drug or toxin induced, associated with HIV infection • Associated with connective tissue disease • Associated with congenital heart disease with corrected systemic-to-pulmonary shunts |
| *Antithrombotic medication at baseline | 
 • No antithrombotic medication • Presence of antithrombotic medication |

*For both STS (A302+A303) and OLS, these variables should be re-baselined according to Sections 6.3 and 5.1.5

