3.2.3 Exclusion criteria

1. Pediatric patients (i.e., < 18 years of age).
2. Patients who are not able to perform Visit 1 of AC-065A303/GRIPHON OL within 2 weeks (i.e., 14 days) of the last visit in AC-065A302/GRIPHON.
3. Patients who have started receiving prostacyclin (epoprostenol) or prostacyclin analogs (i.e., treprostinil, iloprost, beraprost) since the last study drug intake in AC-065A302/GRIPHON⁴.
4. Severe hepatic impairment (Child-Pugh C)
5. Females who are pregnant or who plan to become pregnant during the study or are breast-feeding.
6. Any known factor or disease that might interfere with treatment compliance, study conduct or interpretation of the results, such as drug or alcohol dependence, or psychiatric disease.
7. Known hypersensitivity to selexipag or any of the excipients.

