3.2.4 Concomitant medications

3.2.4.1 Allowed concomitant medications

PAH-specific therapies including ERAs, PDE-5 inhibitors, and/or riociguat.

Concomitant use of inhaled, i.v., and s.c. prostacyclin and prostacyclin analogs (e.g., epoprostenol, treprostinil, iloprost) is permitted, as deemed medically indicated by the

³ A woman is considered to have childbearing potential unless she meets at least one of the following criteria:

- previous bilateral salpingo-oophorectomy or hysterectomy
- premature ovarian failure confirmed by a specialist gynecologist
- pre-pubescence, XY genotype, Turner syndrome, uterine agenesis
- age > 50 years with amenorrhea for at least 24 consecutive months prior to screening

⁴ Single administration of i.v./inhaled prostacyclin or analogs used for acute vasodilator testing during a RHC procedure is allowed.

investigator, to stabilize a patient with worsening of PAH or to switch a patient to i.v. or s.c. treatment.

If a patient is scheduled for an intervention that may temporarily prevent him/her from taking oral medications, it is allowed to interrupt selexipag treatment and temporarily switch to another IP receptor agonist medication with a more convenient route of administration with regard to the patient's medical condition. The patient will be allowed to restart selexipag once he/she can take oral medications again. When re-starting selexipag, it is recommended to begin with the lowest dose (i.e., 1 tablet/200µg b.i.d.) and to progressively increase the selexipag dose to reach the maximum dose that was previously tolerated by the patient. The decrease of the other IP receptor agonist dose will be done in parallel with the increase of selexipag dose based on patient's individual tolerability. If the patient experiences pharmacological side effects that cannot be tolerated while he/she is concomitantly taking selexipag and the other IP receptor agonist medication, a dose reduction or stop of this other IP receptor agonist will be considered before considering a dose reduction or a stop of selexipag.

Single administration of i.v./inhaled prostacyclin or analogs used for acute vasodilator testing during a right heart catheterization (RHC) procedure is allowed.

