- All categories of TE-AEs will be summarized by SOC and PT, whereby the PT “Disease Progression” is only reported, if it is the only PT that the respective AE is coded to. The categories of All TE-AEs, TE-SAEs and SAEs will also be summarized by PT. An overall summary of all TE-AE categories will be provided. This will include the TE-AEs associated with COVID-19 infection. TE-AEs associated with COVID-19 infection will be reported for OLS only.
- The exposure-adjusted incidence rate (EAIR) will be summarized by SOC and PT. TE-EAIR is defined as the number of participants exposed to the intervention and experiencing a certain event divided by the total exposure duration of all participants who are at risk for the event. Specifically, for participants with no such event, the at-risk exposure duration is calculated from the Day 1 to EOT + 3 days; for participants with at least one event of a certain SOC or PT, the at-risk exposure duration is calculated from Day 1 to the first onset of such event.
- The TE-AE summaries above will also be reported for subgroups by PAH medication at baseline - Group 1 (defined in Section 5.6.8).
- TE-Serious AEs will also be summarized, by SOC and PT. In addition, serious TE-AEs will be summarized for subgroups by PAH medication at baseline - Group 1 (defined in Section 5.6.8).
- TE- AEs leading to discontinuation of study intervention will also be summarized, by SOC and PT. In addition, they will be summarized for subgroups by PAH medication at baseline - Group 1 (defined in Section 5.6.8).
- Severe TE-AE will also be summarized, by SOC and PT. In addition, severe TE-AEs will be summarized for subgroups by PAH medication at baseline - Group 1 (defined in Section 5.6.8).
- Related TE-AE will also be summarized, by SOC and PT. In addition, related TE-AEs will be summarized for subgroups by PAH medication at baseline - Group 1 (defined in Section 5.6.8).
- TE- AEs leading to fatal outcome will also be summarized, by SOC and PT. In addition, they will be summarized for subgroups by PAH medication at baseline - Group 1 (defined in Section 5.6.8).
- TE-Serious AEs associated with COVID-19 infection will also be summarized, by PT. The summary will report data from OLS only.
- TE-AEs associated with COVID-19 infection leading to death will be summarized too, by PT and for OLS only.

Listings of all AEs, SAEs and AEs with fatal outcome will be generated, separately, for STS (A302+A303) and OLS.

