5.5.3.1.1. Abnormalities in liver function test results

Additional analyses for TE abnormalities in liver function tests will be performed.

Definition: Additional abnormalities in liver function tests are defined as follows (the “and” conditions do not require concomitant values):

- AST > 3 × ULN or ALT > 3 × ULN
- AST > 5 × ULN or ALT > 5 × ULN
- AST > 8 × ULN or ALT > 8 × ULN
- ALT > 3 × ULN and total bilirubin > 2 × ULN
- (AST > 3 × ULN or ALT > 3 × ULN) and total bilirubin > 2 × ULN.

Abnormality criteria will be applied to baseline and post-baseline values.

Population: All participants included in the STS (A302+A303) and OLS

Study Intervention: Selexipag

Outcome measures: Abnormalities in liver function tests.

Summary method(s) for outcome measure:

- Number and percentage of participants with TE abnormalities
- Abnormalities in liver function tests will also be reported for subgroups by PAH medication at baseline - group 1 (defined in Section 5.6.8).
- A listing and an eDISH plot will be produced to show possible cases as specified in the 4th and 5th abnormalities numbered items. Separate listings and eDISH plots will be produced for STS and OLS.

Separate listings of markedly abnormal values of ALT and AST will be provided for STS (A302+A303) and OLS.

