6.3. Appendix 3 Demographics and Baseline Characteristics

Table 9 lists the demographic variables that will be summarized.

Table 9: Demographic Variables

| Continuous Variables | Summary Type |
|---|--|
| ^Age (years) | Descriptive statistics (N, mean, standard deviation [SD], median and range [minimum and maximum], and IQ range). |
| ^Weight (kg) | |
| Height (cm) | |
| ^Body Mass Index (BMI) (kg/m ²) | |
| ^6MWD (m) | |
| ^NT-proBNP (ng/L) | |
| ^Time since diagnosis (years) | |
| Categorical Variables | Frequency distribution with the number and percentage of participants in each category. |
| ^Age (<18 years, 18-64 years, 65-74 years, 75-84 years, and ≥85 years) | |
| Sex (male, female) | |
| Race/ethnicity (Caucasian /Hispanic, Asian, Black, Other) | |
| Geographical regions (Asia, Eastern Europe, Western Europe + Australia, North America, Latin America) | |
| ^BMI (underweight <18.5 kg/m ² , normal 18.5-<25 kg/m ² , overweight 25-<30 kg/m ² , obese ≥30 kg/m ²) | |
| Etiology (Idiopathic (IPAH), Heritable (HPAH), Drug or Toxin Induced, Assoc. with Connective Tissue Disease, Assoc. with Congenital Heart Disease, Associated with HIV Infection) | |
| ^WHO-FC (I, II, III, and IV) | |
| ^Concomitant PAH medication at BL (None, ERA alone, PDE5i alone, ERA+ PDE5i)* | |
| ^NT-proBNP (low <300 ng/L, medium 300 =< - =< 1400 ng/L, high > 1400ng/L) | |
| ^Number of low-risk criteria met at baseline (0, 1, 2, 3)** | |
| ^Antithrombotic medication at baseline | |

^a If multiple race categories are indicated, the Race is recorded as 'Other'.

*Details of PAH medication at baseline are presented in Section 6.5.

**Low risk criteria met at baseline are: NT-proBNP < 300 ng/L, WHO functional class equal to I/II, 6MWD > 440m.

^For both STS (A302+A303) and OLS, these variables should be re-baselined according to Section 5.1.5.

Some baseline characteristics (specified with symbol ^ in Table 9 above) should be re-baselined according to the analysis set used: for STS (A302+A303), baseline covariates were assessed prior to the start of selexipag; for OLS they were assessed prior to the start of selexipag in A303 (Section 5.1.5). Especially for age, the following formula will be used: age in years at A302 screening date – year of A302 screening date + year of A303 start of intervention.

Demographic variables will be summarized separately for STS and OLS. For OLS, they will be summarized showing all treatment sequences:

| | Treated Set - OL (A303) ^ | | | | | |

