6.5. Appendix 5 Prior and Concomitant Medications

Prior and Concomitant medications will be coded using the World Health Organization Drug Dictionary (WHO-DD). These medications are recorded on the ‘Previous/Concomitant Medication’ pages of the A302 and A303 CRF. Prior medications are defined as any therapy used before the day of the first dose of study intervention. Concomitant medications at baseline are defined as any therapy started on the same day as the first dose of study intervention, or before and continued after the first dose of study intervention. Concomitant medications started during intervention are defined as any therapy started after the day of the first dose of study intervention (excluding medication started after the end of study intervention). Handling missing data is defined in Section 6.5.1.

For A302 general prior medications and concomitant medications were already reported in the A302 CSR. General concomitant medications in A303 are not of interest and will not be summarized. Only listings of all concomitant medications at baseline or started during study intervention will be generated separately for OLSs and STS (A302+A303).

Concomitant PAH-specific medications will be summarized by ingredient name and PAH-specific medication group name (Table 10) using grouping 1 and 2 as defined in Section 5.6.8. For each of the following 2 types of concomitant PAH-specific medications, summary of OLS and STS (A302+A303) will be presented in the same table according to Section 4.

- Concomitant PAH-specific medications at baseline, i.e., any therapy used on the same day as the first dose of study intervention and might continue after the first dose of study intervention). For the STS (A302+A303), baseline refers to the first dose of selexipag either in A302 (participants who received selexipag in A302) or in A303 (participants who received placebo in A302).
- Concomitant PAH-specific medications started during study intervention.

Listings of PAH specific concomitant medications at baseline or started during study intervention will be generated separately for OLS and STS (A302+A303).

Additionally, the following will be summarized separately for OLS and STS (A302 + A303):

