- Number of participants who added a post-baseline new class of PAH-specific medication. A post-baseline new class of PAH-specific medication is defined as any new class of PAH therapy (i.e., ERA/PDE5-i/sCG stimulator/Prostacyclin and analogs only; ERA+PDE5-i; ERA+sCG stimulator; ERA+Prostacyclin and analogs, PDE5-i+sCG stimulator, sCG stimulator+Prostacyclin and analogs, etc.) started after baseline (see Section 5.1.5 for the definition of baseline for STS and OLS).
- Duration of exposure in years (i.e., sum of total exposure duration and mean) before, after and without adding a post-baseline new class of PAH-specific medication.
- Duration of exposure before and after adding a new class of PAH therapy will be given for participants who added at least 1 post-baseline new class of PAH therapy. Exposure duration before adding a new class of PAH therapy will be computed as (start of new class of PAH therapy - start of treatment) / 365.25; Exposure duration after adding a new class of PAH

therapy will be derived as (end of treatment - start of new class of PAH therapy+1) / 365.25. Duration of exposure without addition of a new class of PAH therapy will be given for the number of participants with (or without) concomitant PAH therapy at baseline minus the number of participants who added at least 1 post-baseline new class of PAH therapy, and will be computed as (end of treatment - start of treatment+1) / 365.25.

Table 10: PAH Specific Therapies

| Group name for the Analysis outputs | Category | Subcategory | Generic names |
|---|---|-----------------|---|
| ERA | Antihypertensives for pulmonary arterial hypertension | ERA | ambrisentan, bosentan, sitaxentan, macitentan |
| PDE5-i | | PDE-5 Inhibitor | sildenafil, tadalafil, vardenafil, udenafil |
| sCG stimulator | | sGC stimulator | riociguat |
| Prostacyclin/prostacyclin agonists | Prostanoids | | epoprostenol, treprostinil, iloprost, beraprost |
| Categories are identified by searching the coded WHODRUG preferred terms for occurrence of any of the ingredient names. E.g., 'Sildenafil' and 'Sildenafil Citrate' will both be assigned to sildenafil and thus both considered as PDE-5 inhibitors. | | | |

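### Do the grouping 1 labels misdescribe participants who also take riociguat or a prostanoid, so that the subgroup needs relabelling?

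*SAP*

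**What the plan says.** SAP Section 5.6.8 defines grouping 1 with four cells. The first is "No PAH-specific medication (ERA or PDE5-I"), and the others are ERA alone, PDE5-I alone, and the combination of the two. The variable is re-baselined for each analysis set. Grouping 2, in the same section, counts drugs over four classes: ERA, PDE5-I, sGC stimulator and prostacyclin.

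SAP Section 6.3, Table 9 repeats the grouping 1 cells in shorter form: "Concomitant PAH medication at BL (None, ERA alone, PDE5i alone, ERA+ PDE5i"). An asterisk on that row refers to Section 6.5 for the details.

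SAP Section 6.5 says "Concomitant PAH-specific medications will be summarized by ingredient name and PAH-specific medication group name (Table 10) using grouping 1 and 2". This covers drugs present at baseline and drugs started during treatment. Table 10 in that section lists riociguat and the prostanoids beside ERAs and PDE5-Is. For added therapy, "A post-baseline new class of PAH-specific medication is defined as any new class of PAH therapy", and its examples span all four classes.

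Grouping 1 is the subgroup variable for the safety tables. Section 5.5.2.1 states "The TE-AE summaries above will also be reported for subgroups by PAH medication at baseline - Group 1", and Section 5.5.3.1.1 states "Abnormalities in liver function tests will also be reported for subgroups by PAH medication at baseline - group 1"; both then cite Section 5.6.8.

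Protocol Section 3.2.4.1 allows "PAH-specific therapies including ERAs, PDE-5 inhibitors, and/or riociguat". Protocol Section 3.2.3 excludes "Patients who have started receiving prostacyclin (epoprostenol) or prostacyclin analogs (i.e., treprostinil, iloprost, beraprost) since the last study drug intake" in A302; riociguat is not in that exclusion.

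**The concern.** The SAP treats four drug classes as PAH-specific, but its main subgroup variable looks at two. A participant on riociguat only would be printed as *None* in Table 9, and one on ERA plus riociguat as *ERA alone*. Grouping 2 would show the same two people as taking one drug and two or more drugs. The SAP's Introduction says the completed summaries can be used to update submission tables, where a reader may take the labels at face value.

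There is also a programming question. If *alone* is read strictly, a participant on ERA plus riociguat has no cell. If it is read loosely, the participant has a cell with an inexact label.

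Finally, Section 6.5 applies grouping 1 to drugs started on treatment. Someone who adds only riociguat or a prostanoid would then seem to have no correct category. If these points had force, the subgroup safety tables would mix background therapies under labels that deny it.

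**Working it through.** The plan states no figure on this point and tests no hypothesis, so there is nothing to reproduce. The check has four steps.

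**1. How many drug combinations carry an inexact label?** Assign each combination of classes to its grouping 1 cell by ERA and PDE5-I status only. Three of the four labels (*None*, *ERA alone*, *PDE5-I alone*) become inexact when any other class is present. The combination label stays true whatever is added.

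| Classes considered | Combinations | Inexact labels |
|---|---|---|
| ERA, PDE5-I | 2² = 4 | 0 |
| plus sGC stimulator | 2³ = 8 | 3 × 1 = 3 |
| plus prostacyclin | 2⁴ = 16 | 3 × 3 = 9 |

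In the last row, the second factor is the number of ways to take at least one of the two other classes: 2² − 1 = 3. Each inexact label also implies a drug count that differs from grouping 2. If the labels said *neither*, *ERA without PDE5-I*, *PDE5-I without ERA* and *both*, 0 of 16 would be inexact. Every combination would stay in the cell it has now.

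**2. Where do the labels appear?** The safety summaries by grouping 1 are:

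- Section 5.5.2.1: 6 (all, serious, discontinuation, severe, related and fatal events)
- Section 5.5.2.3: 1
- Section 5.5.2.4: 1
- Section 5.5.3.1: 2 (abnormalities; descriptive values and changes)
- Section 5.5.3.1.1: 1

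The total is 6 + 1 + 1 + 2 + 1 = 11. All refer to Section 5.6.8, where the first cell carries its bracket. The bare *None* stands only in Table 9. The word *alone* has no qualifier in either place.

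**3. How many participants could be affected at baseline?** The documents give no count. As an assumption, let a share p of the 709 participants treated in A303 be on riociguat or a prostanoid:

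- p = 0%: 0 × 709 = 0
- p = 1%: 0.01 × 709 = 7.1, about 7
- p = 5%: 0.05 × 709 = 35.45, about 35

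These are upper bounds, because anyone also on both ERA and PDE5-I is correctly labelled. Three facts point to the low end, though none proves it. A303 enrolment closed on 02 September 2014 (SAP Section 1.2). The seven approved agents listed in Protocol Section 1.1 do not include riociguat. Recently started prostanoids are excluded at A303 entry. In the combined A302 + A303 set, baseline for the 574 participants given selexipag in A302 is the start of A302. The documents do not give the A302 rules on concomitant drugs.

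**4. Is the information lost?** No. Section 6.5 tabulates baseline PAH drugs for both analysis sets by ingredient, by Table 10 class and by grouping 2. Drugs started on treatment get the same tables, with listings and the new-class summary in addition. The only thing not tabulated is the split of riociguat or prostanoid users across the four grouping 1 cells.

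**The case for a change.** The best case for a change is that the labels are inexact on the SAP's own terms, that the tables may reach regulators, and that new labels cost little. A second argument is that the point about drugs started on treatment does not depend on how many participants took riociguat at baseline, since Protocol Section 3.2.4.1 allows non-oral prostacyclins during A303.

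Part of this stands. *Alone* is not defined, and Table 9 drops a bracket that Section 5.6.8 has. The SAP also does not say where a participant on ERA plus riociguat belongs.

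The rest does not lead to a change:

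- **Programming.** The bracket in the first cell points to the two-class reading. The strict reading would leave some participants in no cell, and the column would then fall short of its total. An analyst would see that and settle on two classes.
- **Drugs started on treatment.** Section 5.6.8 defines grouping 1 as a baseline variable. Section 6.5 can therefore be read as showing newly started drugs within baseline strata, and everyone then has a category. Removing grouping 1 there would discard a legitimate display. Even if it is read as classifying the new drugs themselves, the ingredient, class and new-class summaries still show them.
- **Cost.** Footnoting the other drugs would take a count in each of four cells at two baselines, and total use is already tabulated.

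**Conclusion.** The labels are loose and the concern is literally correct, but nothing in the analysis turns on it. On the two-class reading, relabelling leaves every participant in the same cell and every count, denominator and endpoint unchanged. *None* is at issue in one row of Table 9, and that row refers the reader to the section with the full breakdown. *Alone* could mislead only a reader who ignores both the bracket in Section 5.6.8 and the four-class tables in Section 6.5.

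The number of participants concerned at baseline is unknown and may be zero; the figures of 7 and 35 rest on assumed rates. The study is descriptive, so no inference depends on these subgroups. The conclusion assumes that analysts derive grouping 1 from ERA and PDE5-I status only, as the bracket indicates, and that the Section 6.5 tables are produced as planned. A one-line table note on the meaning of *alone* would be good housekeeping at the programming stage, but it does not require a change to the SAP.
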